The sample size is 40 women prisoners overall. In the prison, there are ~40 active self-harming women prisoners per month (Nov 2013), of whom 25 have closed wounds, and 15-20 are likely to be eligible for camouflage per month. Our two recent consultations with stakeholders in the prison and the phase 1 focus group suggest interest in the intervention is high among women prisoners. 20 women prisoners will be randomised to receive the 6-week intervention; the other 20 women prisoners will be wait-list controls and receive the intervention after study completion. In the focus group with women we explored how they would feel about being randomly allocated to intervention or wait-list control and the women said they would not mind as they would still get to use the products after the research. As piloted in WORSHIP II, we shall censor women by release-date to reduce attrition, and try to follow the few women moved before the end of 6-weeks. If a woman has left prison before the three-month follow-up we will ask the prison to send the follow up letter to the women in the community. The women will have consented to this approach at the start of the research. Follow up in the community will involve completion of the questionnaires via distance methods e.g. email, post or telephone interviews. If a wait-list control woman leaves the prison

before the MSC is provided they will be instructed to contact the research team and will be posted their bespoke skin matched creams and powders.

Phase 4 Inclusion Criteria: Remand and sentenced women prisoners screened for date of release, with at least 6 weeks left on their sentence. The women will have passed the security vetting check which will be carried out by Safer Custody in association with prison officers to ensure that the researchers are safe during the project. The women will have self-harm scarring, with some closed wounds (to allow the MSC to be applied).

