2. Becks Scale for Suicidal Ideation (BSSI): a 19-item instrument measuring intensity, duration and specificity of thoughts about committing suicide. The 19 items are rated on a three-point scale (0-2).
3. Becks Depression Inventory (BDI): a 21-item scale measuring symptoms of depression. Items are rated on a 4-point scale (0-3) with severity of self-reported depression: 0-9 minimal; 10-16 mild; 17-29 moderate and 30-63 severe.
4. Beck Hopelessness Scale (BHS): a 20-item self-report inventory designed to measure three major aspects of hopelessness: feelings about future, loss of motivation and expectations.
5. Deliberate Self-Harm Inventory (DSHI): a 17-item questionnaire giving history and frequency of self-harming behaviours.
6. Prison-adapted Dermatology Quality of Life Index (DLQi): a 7-item questionnaire adapted from a validated 10 item scale that has been used in over 40 different skin conditions in over 80 countries. The DLQi is the most frequently used instrument in studies of randomised controlled trials in dermatology.

7. Rosenberg Self-Esteem Scale: a 10-item Likert scale with items answered on a four-point scale – from strongly agree to strongly disagree. The scale measures self-esteem and has been used in prison research.

6. Incidence and frequency of self-harm will be collected from participant's prison records and the weekly diary.

7. We shall explore acceptability/relevance of two generic preference-based health-related quality of life (HRQoL) measures: The EQ-5D-5L covers five domains of health (mobility, self-care, usual activities, pain/discomfort, anxiety/depression). This new version was developed due to concerns over the lack of sensitivity to change of the original EQ-5D-3L, and consists of five severity levels for each domain (no, slight, moderate, severe, and extreme problems) rather than the original three levels (no, moderate, or extreme problems). Participants' responses are converted to a single index utility value based upon preference weights obtained from a UK general population sample.

SF-12 is a shortened version of the SF-35, consisting of twelve questions covering eight dimensions of health: physical functioning, role limitations - physical, bodily pain, general health, vitality, social functioning, role limitations - emotional, and mental health. A single index utility value is then obtained by applying published SF-6D preference weights.

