8. Members of the prison staff will complete resource use proformas (based on the Secure Facilities Service use Schedule) for all participants and the research team will record including time spent by Changing Faces training the researchers, time spent by trained prisoners delivering the intervention, and quantities of MSC products used and prescribed. Descriptive analysis will inform future trial design.

9. Demographic and relevant personal history will be collected using a bespoke personal history questionnaire, previously used in a prison population in the WORSHIP projects.

As per HMPPS rules and regulations, no incentives or payments can be offered to participants whilst they are residing in the prison. However, the research team will provide an incentive for released women to complete follow-up outcome measures in the community. This will take the form of a £20 gift voucher, as well as reimbursement of travel expenses. This voucher will be given to compensate for their time and effort in coming to the appointment.

Analyses

(1) Feasibility and Acceptability: primarily qualitative (Phases I /4), but includes quantitative assessment of treatment attrition. Verbatim-transcription analysed using thematic content analysis.

(2) Quantitative data: Insufficient power for quantitative hypothesis testing means before and after treatment changes are descriptive including standard deviations and confidence intervals for outcome variables to inform sample size estimates for future RCT and assessment of feasibility of control group retention.

(3) Feasibility of delivering and acceptability and relevance to the prison population of EQ-5D-5L, SF-12 will be assessed through correlation between changes from baseline to follow-up of these and other piloted measures (WEMWBS, SOS-10, PANAS, BSSI, BDI, DSHI); and examination of completion rates. Descriptive analysis of HRQoL data will also be performed to inform the suitability of the measures for future clinical and economic evaluations of MSC in prison.

The resource use proformas will be assessed through time taken to complete the forms, completion rates, and ability to obtain included resource-use categories.

Survey

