7. Modifying with stakeholders the various Scales and piloting their use in prison will benefit this population by validating their use in prison research.
8. Assessing the acceptability and relevance of two generic preference-based health-related quality of life measures; the EQ-5D-5L and the SF-6D, to the prison population will inform the suitability of these measures for use in future clinical and economic evaluations in this setting.

Wider NHS/public benefits:

1. Upon release, when the women prisoners continue to be NHS service-users, women prisoners may become empowered to participate in work and social activities that they otherwise might avoid because of low self-esteem/ self-confidence and the stigma of scarring.
2. The community pilot supports this notion as it suggests positive effects are associated with improved self-esteem, confidence, personal development and activities of daily living/functioning and reduced risk of mental illness or relapse.
3. The risk in the longer term of unemployment and/or days off school/college and the economic burden associated with this in a vulnerable ex-offender population is considerable. Therefore, positive effects on this risk-burden are likely to be significant to the wider public.
4. The study will also increase the evidence-base for using a women- and service-centred approach for developing medical skin camouflage services in the NHS more broadly as well as promoting development of a recovery model to be delivered to women services-users in other settings, such as secure services where self-harm management is a highly significant problem.
5. Barriers and benefits to this recovery intervention identified in the study can be embedded in Safer Custody generic guidance (e.g. Prison Orders) through NOMS partnership working to improve healthcare delivery for self-harm recovery within women's prisons.

Data Management

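### Change-score correlations are listed as evidence on the feasibility, acceptability and relevance of EQ-5D-5L and SF-12, but they speak only to responsiveness, and two named comparators are not collected

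*Combined protocol and SAP*

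**What the plan says.** Analyses (3) names the properties to be assessed: "Feasibility of delivering and acceptability and relevance to the prison population of EQ-5D-5L, SF-12". These "will be assessed through correlation between changes from baseline to follow-up of these and other piloted measures", with six comparators listed: WEMWBS, SOS-10, PANAS, BSSI, BDI and DSHI. The same sentence adds a second method, "and examination of completion rates". The next sentence adds a descriptive analysis of the quality-of-life data, to help decide whether the measures suit later clinical and economic evaluations.

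The aim appears twice more. In the Outcome measures list, the second item numbered 7 says "We shall explore acceptability/relevance of two generic preference-based health-related quality of life" measures. Item 8 under Benefits of the study begins "Assessing the acceptability and relevance of two generic preference-based health-related quality of life measures".

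On size, the Recruitment & Participants section says "The sample size is 40 women prisoners overall" and "20 women prisoners will be randomised to receive the 6-week intervention; the other 20 women prisoners will be wait-list controls". Analyses (2) disclaims testing: "Insufficient power for quantitative hypothesis testing means before and after treatment changes are descriptive including standard deviations and confidence intervals".

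Analyses (3) gives no threshold for a correlation or a completion rate and no type of correlation. It does not say whether follow-up means the 6-week assessment or the one 3 months after it.

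**The concern.** Three properties are paired with two quantitative methods, and the text does not say which method answers which question. A correlation between changes is evidence on shared responsiveness: when one scale moves, does the other move too? It cannot show whether women are able or willing to complete EQ-5D-5L or SF-12, and it is at best indirect evidence that the content is relevant to them. It can be computed only in women with both scales at both time points, so those who decline, skip items or drop out do not contribute. They carry much of the information on acceptability.

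The choice of outcomes for a future randomised trial is one of the protocol's research questions, and this analysis is meant to inform it. If change correlations are reported under the label of acceptability or relevance, a noisy low value could count against a usable instrument, and a high value among completers could be taken as reassurance that it does not give.

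The comparator list adds a practical problem, because two of the six scales are not in the assessments as planned.

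**Working it through.** **1. Inputs.** N = 40, allocated 20:20 (Recruitment & Participants). The documents give no expected correlation, confidence level, dropout rate, scale reliability or score stability. Every such value below is an assumption. There is no power or precision figure in the plan to reproduce.

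**2. Which method bears on which property.**

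| Method in Analyses (3) | Who contributes | What it informs |
|---|---|---|
| Change-score correlation | Only women with both scales at both times | Responsiveness; relevance only indirectly |
| Completion rate | All women due an assessment | Feasibility directly; acceptability in part |
| Descriptive quality-of-life analysis | Women with scores | Suitability in general; content not specified |

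The plan uses a closer match for the resource-use proformas. They are judged by how long they take, how often they are completed and whether each category can be obtained.

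**3. Precision of a correlation.** The 95% interval is tanh(atanh(r) ± 1.96/√(n−3)). For n=40 the half-width on the z scale is 1.96/√37 = 0.322. At r=0.30, atanh(r) = 0.310, so the limits are tanh(−0.013) = −0.01 and tanh(0.632) = 0.56.

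| Women with both assessments | r=0.30 | r=0.50 | r=0.70 |
|---|---|---|---|
| 40 (no loss) | −0.01 to 0.56 | 0.22 to 0.70 | 0.50 to 0.83 |
| 30 (25% loss, assumed) | −0.07 to 0.60 | 0.17 to 0.73 | 0.45 to 0.85 |
| 20 (50% loss, assumed, or one arm) | −0.16 to 0.66 | 0.07 to 0.77 | 0.37 to 0.87 |

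The smallest |r| whose interval excludes zero is 0.31, 0.36 and 0.44 for n = 40, 30 and 20.

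**4. Possible attenuation.** Take two scales with the same reliability and stability and equal variance at both times. Then change-score reliability = (reliability − stability)/(1 − stability), and observed r = true r × reliability. Assume reliability 0.80 and a true correlation of 0.60, the same for levels and for changes. The baseline correlation is then 0.60 × 0.80 = 0.48.

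| Stability (assumed) | Change-score reliability | Observed change correlation |
|---|---|---|
| 0.70 | 0.10/0.30 = 0.33 | 0.20 |
| 0.60 | 0.20/0.40 = 0.50 | 0.30 |
| 0.40 | 0.40/0.60 = 0.67 | 0.40 |
| 0.20 | 0.60/0.80 = 0.75 | 0.45 |

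The loss relative to 0.48 runs from 0.03 to 0.28, depending on a figure that the documents do not give.

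**5. The alternatives are not precise either.** A baseline r of 0.48 with 40 women has a 95% interval of about 0.20 to 0.69. A completion rate of 32/40 (80%) has a Wilson 95% interval of 0.65 to 0.90, and 36/40 (90%) has 0.77 to 0.96.

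**6. Comparators.** The Phase 4 Outcome Measures section lists the same ten scales at baseline and at both follow-ups: DSHI, BSSI, BHS, BDI, EQ-5D, SF-12, WEMWBS, Rosenberg, DLQI and the personality-disorder scale. SOS-10 and PANAS are not among them, so only four of the six named comparators can be used. BHS, Rosenberg and DLQI are collected but not named in Analyses (3).

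**The case against.** The strongest reply is that the plan does not rest these judgements on correlation alone. Completion rates stand in the same sentence, and descriptive analysis follows. A natural reading gives completion rates to feasibility and acceptability, and correlations to relevance. That reading is fair, but it has to be supplied by the reader, and one clarifying sentence would settle it.

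Second, change correlations have a real use here. The Outcome measures list says that the five-level EQ-5D was developed because its predecessor responded poorly to change, and economic evaluations depend on change. Baseline correlations cannot show that. This stands, and it is why the change correlations should be kept.

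Third, no accept-or-reject rule is set, and Analyses (2) openly disclaims power. A reader might infer that an instrument would be kept or rejected on a correlation. The documents contain no such rule, and a poorly completed scale would show in the completion rates. Misreading is a risk and not a built-in consequence.

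A reader might also infer that change in the wait-list half must be mostly measurement error. The documents do not support that. A correlation needs women to differ in how much they change, not a treatment effect, and untreated women can change; the diary itself records life events that affect self-harm.

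**Conclusion.** The concern holds in a limited form. Change-score correlations do not measure feasibility or acceptability at any sample size, and Analyses (3) should not list them as evidence on those properties without saying what each method is for. They are also imprecise for weak to moderate values with 40 women or fewer, and may be attenuated: from 0.48 at baseline to between 0.45 and 0.20 on changes, under reliability 0.80, a true correlation of 0.60 and stability from 0.20 to 0.70. All of those values are assumed, and the size of the gap rests mainly on stability. That SOS-10 and PANAS cannot be used follows from the documents without assumptions.

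A reader might conclude that such correlations are close to uninformative in 40 women. That goes too far: r=0.50 gives 0.22 to 0.70, r=0.70 gives 0.50 to 0.83, and r=0.50 excludes zero even with 20 women. Baseline correlations would be imprecise too. Their advantage is that they avoid follow-up attrition and the possible attenuation. This is a modest but worthwhile improvement to an exploratory analysis.

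**What to change.** In Analyses (3):

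- Base feasibility and acceptability of EQ-5D-5L and SF-12 on completion rates at each time point, item-level missingness, and floor and ceiling percentages.
- Add baseline cross-sectional correlations in all randomised women, with 95% intervals, against scales actually collected (WEMWBS, BSSI, BDI, BHS, DSHI, Rosenberg, DLQI). Present these as the evidence on relevance, in the sense of convergent validity.
- Keep the change-score correlations, with 95% intervals, as evidence on responsiveness only. State the type of correlation and which follow-up is used, and draw no feasibility or acceptability conclusion from them.
- Remove SOS-10 and PANAS from the comparator list, since neither is in the planned battery.

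The cost is a few sentences and a few tables from data already planned. Interview data should be cited for the acceptability of the questionnaires only if the topic guides already cover them. The Qualitative follow-up section describes the interviews and the staff focus group as covering the intervention, the training and the practitioner role, and the guides themselves are not in the documents.
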